The main objective of this project will be to identify inflammatory reduction biomarkers linked to MAPK-dependent alterations after CBD administration, as well as other systemic effects on cell signaling pathways. Investigating the role of cell-specific biomarkers describing the molecular response to CBD-administration may open avenues for additional therapeutic strategies that can help reduce the burden of chronic musculoskeletal pain and other pain-related symptoms and comorbidities in people living with HIV (PLWH). The team proposes to study the effects of CBD on inflammation and chronic pain in PLWH by enrolling five persons with HIV who will provide blood samples before and after taking CBD for two months. In the process, the goal will be to establish the molecular role(s) of different immune cells using single cell RNA-sequencing. Preliminary data from this study are expected to pave the way for further investigations in larger clinical cohorts. The primary aim of this project will be to identify key inflammatory reduction biomarkers linked to MAPK-dependent alterations after CBD administration. Secondary outcomes include pain relief and reductions in pain-related symptoms. We will use a prospective pilot study design where patients will self-administer the investigational product (CBD-extract) for 60-days (2 months).

Specific Aim #1 – Determine the effects of CBD on chronic on quality of life in PLWH. We will compareQuality of Life (QoL) measures between treatment conditions, including pain and pain-related symptoms, if present.

Specific Aim #2 – Determine key biobehavioral mechanisms contributing to antiinflammatory and analgesic effects of CBD administration in PLWH. We hypothesize that change in molecular (alterations in cell signaling and reduction in inflammatory cytokines), psychological (reduction in pain-related fear and pain catastrophizing), and pain sensitivity regulation measures will be associated with pain relief, inflammation reduction, and reservoir shrinkage. We will quantify the shift in anti-inflammatory macrophage/monocyte population caused by CDB administration by examining gene expression at the single-cell level from the PBMC samples. This will allow us to accurately pinpoint gene under- or over-expression patterns at the RNA level (biomarkers), that are both induced by CBD administration in PLWH, and specific to different cells (e.g., monocytes, T cells, B cells, or other immune cells).

6. Research Plan

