Motivation to study single cells. The molecular and cellular changes underlying the inflammation mitigation caused by CBD-administration are largely unknown, and stand as a major challenge both for understanding its basic biology (e.g., pathways involved, molecular mechanisms) and for the urgent unmet need of reducing the long-term harm chronic inflammation causes in PLWH. Our hypothesis is that CBD alters monocyte migration capacity with MAPK-dependent alterations. We expect this alteration to have

chain-effects based on cellular cross-talk, i.e., that different PBMC cell types (such as Tcells and B-cells) might express specific CBD-induced phenotypes. We hypothesize CBD-alterations to reverberate along the whole immune-modulation system through cellular cross-talk. Given the complexity of the immune response, we deem traditional (bulk) RNA sequencing as insufficient for the task. Population-averaged genomic profiling cannot adequately unravel the inter-cellular regulation in situ. This study will leverage the efficiency of newly available single-cell technologies to create a powerful dataset unveiling the functional properties of thousands of individual cells.

Sample collection and processing. We plan to collect samples from five to seven patients over three time points: baseline (no CBD), and after one and two months of CBD-administration with 5,000 cells sequenced per sample. Five to seven patients (15 to 21 samples) will provide the transcriptomes of 75,000-105,000 single cells, a large dataset for scRNAseq. Immediately after collection, samples will be collected by TBD Lab technician to be processed for scRNAseq at UF ICBR (PBMC scRNAseq experiments are routinely run at ICBR).

Data analysis. During the post-processing period, single-cell reads (count matrices) will be filtered for quality control. Unsupervised clustering will isolate statistically robust populations of similar cells. Clusters will be visualized using Principal Component Analysis (PCA), t-Distributed Stochastic Neighbor Embedding (tSNE), and Uniform Manifold Approximation and Projection (UMAP). The most informative gene expression markers will be identified by a host of non-parametric tests (e.g., the Kolmogorov–Smirnov test), comparing a given cluster against either a nearby cluster or all other clusters. Clusters of cells will be annotated by using their marker genes/pathways⁻ and prior biological knowledge to characterize each sample's cell composition.

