CBD biomarker extraction. We will contrast clusters of the same cell type at baseline (no CBD) and their counterparts after CBD administration. The difference in gene expression, measured in fold change, p-value, and ratio of cell fraction expressing the marker gene, will determine the phenotypic effect of CBD. For each cell type, we expect to extract one or more sets of CBD-specific candidate biomarkers that together will determine a phenotypic CBD per cluster (cell type) signature.

Investigational Product & Dosing Schedule. [name] (Co-I) will oversee CBD dosage and administration.We will source the investigational product from the same batch of our hemp-extract CBD product that is being used in the original protocol under IND 147985, 'Efficacy of a controlled short-term trial of Cannabidiol (CBD) ingestion on reducing symptomatic response and facilitating recovery after induced muscle injury' (Source: SunFlora, Inc, [name])''. SunFlora is a third-party tested hemp-derived product manufacturing company. SunFlora is dedicated to producing high quality hemp-derived products formulated to be safely used by the public and are manufactured in accordance with the Food and Drug Administration (FDA) Current Good Manufacturing Practices (cGMP) for Dietary Supplements, 21 CFR Part 111. Their hemp derived products are assessed multiple times at production process control points throughout the manufacturing process. Dietary ingredients used in the manufacturing process are accompanied by certificates of analyses (CoAs) confirming their identity and specifications. All finished products are tested to ensure they meet specifications prior to being released for distribution. The label and all labeling satisfy FDA requirements found under 21 CFR 101.

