Each participant will be provided two 30mL bottles (2000mg CBD per bottle) with a syringe dropper during their initial (baseline) visit with instructions/demonstration to administer the solution under the tongue (0.5 cc ~1/2 dropper) twice per day (BID) 8-12 hours apart (morning and evening) at the prescribed daily dosage (63mg/day). The sublingual route of administration allows the product to be absorbed directly into venous circulation, and thus bypasses the liver and eliminates the consequences of first pass metabolism; ultimately increasing its bio-availability. The bioavailability of CBD administered orally (including sublingual) is estimated to be 13-19% and its half-life estimated to be around 18-32 hours.

Physical Discomforts and Intervention Risks:

In previous clinical trials using hemp-derived products administered orally (liquid or capsule) and swallowed, a small percentage of patients experienced tiredness, change in appetite and gastro-intestinal discomfort following ingestion. We will be using daily doses of hemp extract that are considerably lower than the daily doses used in the clinical trials. Therefore, the chance of our participants experiencing these side effects is minimal.

Occasionally one or more of the following potential side effects of taking blood samples may occur: pain, bruising, slight bleeding, light-headedness, fainting and (rarely) an infection. A trained technician will be drawing the blood.

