Screening: Study coordinator will screen candidate to determine if they meet the inclusion criteria for the study. The baseline visit activity will be described to the patient. The patient will sign the consent form. Instruction/demonstration about CBD and dropper use will be provided.

Visit 1: Baseline Evaluation before CBD administration

Activities during visit 1:

- Patient reads and signs the consent form.
- Patient completes a brief form providing information (e.g. age, address, phone number, etc., health history).
- Measure of patient's height, weight, and vital signs (HR, blood pressure, body temperature).
- Patient completes a urine drug test
- Patient completes a urine pregnancy test is they have the ability to become pregnant
- Patient fills questionnaires: PASS (Pain Anxiety Symptom Scale; four dimensions of pain measured: cognitive anxiety, escape/avoidance, fearful appraisal, physiological anxiety), VAS (Pain Experience Visual Analogue Scales; anxiety, depression, anger), PSQI (Pittsburg Sleep Quality Index; self-report used to assess a subject's usual quality of sleep)
- A trained nurse or technician draws a blood sample
- The patient is given 2 30mL bottles with a syringe dropper with instructions/demonstration to take the solution under the tongue (0.5 cc ~1/2 dropper) twice per day (BID), 12 hours apart (morning and evening), at the prescribed daily dosage (62.5mg/day).
- The patient schedules the next test visits to the laboratory.
- The patient receives \$100 for completing this visit.

Visit 2: Follow-up after a month period of CBD administration

Activities during visit 2 (day 26-34):

- Measure vital signs of the patient as in visit 1.
- Questionnaire filling as in visit 1.
- Blood draw as in visit 1.
- The patient schedules the next test visits to the laboratory.
- The patient receives \$100 for completing this visit.

Visit 3: Follow-up after a two-month period of CBD administration

Activities during visit 3 (day 56-64):

- Measure vital signs of the patient as in visit 1.
- Questionnaire filling as in visit 1.
- Blood draw as in visit 1.
- The patient schedules the next test visits to the laboratory.
- The patient receives \$100 for completing this visit.

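### The written product and volume deliver 66.7 mg of CBD a day, not the stated 63 or 62.5 mg; the plan should say whether the mg or the mL governs, because the length of the supply depends on it.

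*Combined protocol and SAP*

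**What the plan says.** Section 6 of the combined protocol and SAP, under Investigational Product & Dosing Schedule, describes the supply: "Each participant will be provided two 30mL bottles (2000mg CBD per bottle) with a syringe dropper". Participants are told to "administer the solution under the tongue (0.5 cc ~1/2 dropper"), and to do so "twice per day (BID) 8-12 hours apart (morning and evening) at the prescribed daily dosage (63mg/day").

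Under Experimental Procedures, the Visit 1 list has the same two 30 mL bottles and the same 0.5 cc, but the instruction reads "twice per day (BID), 12 hours apart (morning and evening), at the prescribed daily dosage (62.5mg/day"). Bottles are handed out at visit 1 only; the activities for visits 2 and 3 include no dispensing.

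On duration, section 5 (Specific Aims) says that "patients will self-administer the investigational product (CBD-extract) for 60-days (2 months"). The last blood draw falls under "Activities during visit 3 (day 56-64"). The plan does not say whether a participant seen after day 60 should still be dosing.

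The dosing section also gives an estimated CBD half-life of 18-32 hours. The Safety Monitoring text provides a daily dose log, weekly calls about missed doses, and photographs of the bottles at about days 15 and 45 to check the liquid level.

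**The concern.** The plan states the same regimen as a volume and as a daily mass, and the two disagree. It also gives two different masses. A reader cannot tell which dose is prescribed, and if participants follow the volume, the study will report a dose lower than the one taken.

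The choice also fixes how long the dispensed oil lasts, and so whether the visit 3 window can run past the supply. Samples are planned "after one and two months of CBD-administration with 5,000 cells sequenced per sample", and the biomarker analysis is described this way: "We will contrast clusters of the same cell type at baseline (no CBD) and their counterparts after CBD administration". With 5-7 patients and only two post-baseline draws each, it matters whether the month-2 samples were all taken under the same exposure. Finally, the liquid-level photographs have no single expected level to be read against.

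**Working it through.** **Inputs.** Two bottles, 30 mL and 2,000 mg each, so 60 mL and 4,000 mg (dosing section). 0.5 mL twice daily, so 1.0 mL/day (dosing section and Visit 1). Stated dose 63 mg/day (dosing section) and 62.5 mg/day (Visit 1). Course 60 days (section 5). Visit 3 on days 56-64. Half-life 18-32 h (dosing section).

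**Trying to reproduce the stated dose.**
- Concentration = 2,000 mg / 30 mL = 66.67 mg/mL.
- Per dose = 66.67 x 0.5 = 33.3 mg. Per day = 66.67 x 1.0 = 66.7 mg.
- Against 63: 66.67/63 - 1 = 5.8% above (63 is 5.5% below 66.67).
- Against 62.5: 66.67/62.5 - 1 = 6.7% above (62.5 is 6.25% below 66.67).

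Other readings do not recover the figure. A US fluid-ounce bottle (29.57 mL) gives 67.6 mg/day, and 2,000 mg shared across both bottles gives 33.3 mg/day. Reaching 62.5 mg/day at 1 mL/day needs a 32 mL bottle, or 1,875 mg in 30 mL; the plan states neither.

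**Supply under each reading.**

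| What governs | mL/day | mL per dose | Days of supply |
|---|---|---|---|
| 0.5 mL twice daily | 1.000 | 0.500 | 60 / 1.0 = 60.0 |
| 63 mg/day | 63 / 66.67 = 0.945 | 0.4725 | 4,000 / 63 = 63.5 |
| 62.5 mg/day | 62.5 / 66.67 = 0.9375 | 0.469 | 4,000 / 62.5 = 64.0 |

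**Bottle-level check.** Expected use by day 15 is 15.0 mL if the volume governs and 15 x 0.9375 = 14.1 mL at 62.5 mg/day. By day 45 it is 45.0 against 42.2 mL. The 2.8 mL difference at day 45 equals between five and six 0.5 mL doses, so a participant measuring out 62.5 mg/day exactly could look as if doses had been missed.

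**Visit 3, if the volume governs.** 60 mL / 0.5 mL = 120 doses. At 12 h spacing with none missed, dose 120 falls 119 x 12 h = 59.5 days after the first. The last dose then lands between the evening of day 59 (baseline is day 0, both doses taken that date) and the evening of day 61 (baseline is day 1, first dose the next morning). A draw late in the window can therefore follow the end of the oil by up to about 4 days.

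**Drug remaining**, assuming simple exponential decline at the plan's half-life, 0.5^(hours / half-life):
- 24 h after the last dose: 0.5^(24/18) = 40% to 0.5^(24/32) = 59%.
- 96 h after the last dose: 0.5^(96/18) = 2.5% to 0.5^(96/32) = 12.5%.

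These are fractions of drug. The plan gives no time over which gene expression returns to its untreated state, so the effect on the month-2 contrast cannot be computed.

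**The case against.** The strongest reply is that the volume may be the inexact figure. Both places call the mg figure the prescribed dosage, the volume carries an approximate dropper mark, and 63 looks like 62.5 rounded. On that reading 0.5 cc is a rounding of about 0.47 mL and the oil lasts to day 64, the end of the window. This stands, and it is why the supply point can only be conditional. It does not remove the inconsistency: dropper imprecision explains variation in what is taken, but not two prescribed figures that both disagree with the nominal product.

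On the other reading, 60 days of oil matches the 60-day course, and nothing in the plan requires the last draw to be taken on product. That also stands. The plan is silent on dosing after day 60; it does not break a rule of its own.

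A reader might infer more than the documents support:
- That 66.7 mg/day is the true dose and must be adopted. The plan does not say which quantity governs, so the review cannot choose.
- That late month-2 samples are drug-free or biased. Shortly after the last dose much of the drug remains (40-59% at 24 h); only draws near day 64 approach washout, and only with full adherence and exact doses. Missed doses stretch the supply, while spillage shortens it.
- That more oil must be dispensed. Scheduling deals with the gap at no product cost, and the batch is shared with another protocol.
- That the two dosing intervals conflict. Twelve hours lies within 8-12 hours, so the difference is slight.

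The existing log, calls and photographs would also show the supply running low before visit 3. They do not settle which dose was intended.

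**Conclusion.** The stated daily dose is inconsistent with the stated product and volume. As written, the regimen delivers 66.7 mg/day (33.3 mg per dose), and the stated figures are 5.5% to 6.3% below that. This rests only on the plan's own numbers.

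The visit 3 gap is a conditional note. It arises if the volume governs, the participant misses no doses, and the draw falls on days 61-64; the exact days depend on day numbering and the time of the first dose, which the plan does not give. If 62.5 mg/day governs there is essentially no gap.

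Severity is minor. The mg/day figure does not enter the analysis, no safety consequence follows from the documents, and the month-1 sample (days 26-34) is unaffected.

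**What to change.** 1. State which quantity governs and correct the other in both the dosing section and the Visit 1 list. Either 0.5 mL twice daily = 66.7 mg/day (60 mL lasts 60 days), or 62.5 mg/day = about 0.47 mL twice daily (60 mL lasts 64 days).
2. Use that volume as the reference for the day 15 and day 45 bottle-level checks.
3. If the volume governs, schedule visit 3 by day 60 where possible, but keep the day 56-64 window so that no sample is lost. Record the date and time of the last dose at each post-baseline draw, using the existing daily log.

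The cost is a wording change in two places and one extra data field at visits 2 and 3. The small downside is tighter visit 3 scheduling. No extra oil is needed.

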Study Population. Our clinical population will be men and women (N=5 to 7) 21-60 years old who are currently living with HIV (under antiretroviral therapy for 5+ years with a suppressed viral load).

Recruitment strategy. Co-I [name] has extensive experience in HIV patient recruitment and will oversee the recruitment team, during the recruitment phase, as well as the safety monitoring. Five PLWH (men and women) will be primarily recruited from The SHARC Registry (IRB# 201400073), a UF-IRB-approved registry of over 600 HIV patients who have agreed to be contacted about future research. Written informed consent will be obtained, and blood will be collected at the UF CTRB clinical research center. Inclusion criteria are: ability to read English and provide written consent; willingness to take CBD and to participate in follow up for two months; older than 21 and younger than 60; under antiretroviral therapy for 5+ years and suppressed viral load (CD4 count <350cells/ml); patients must agree to practice acceptable methods of birth control, namely sterilization (female tubal ligation or occlusion, male vasectomy), long-acting reversible contraceptives (intrauterine devices, hormonal implants), short-acting hormonal methods (pill, mini pills, patch, shot, vaginal ring), and condoms.

The main exclusion criterion will be conditions/medications that may impair the immune response (e.g. rheumatoid arthritis, cancer, diabetes chronic infections, CAD, cellulitis, autoimmune diseases such as lupus, sarcoidosis, and all medications they may affect inflammation such as aspirin, steroids, statins);), pregnancy, and current marijuana or CBD use (urine drug screen). Further exclusion criteria will be: excluding subjects taking anti-seizure medicines, with any history of seizure disorder or head trauma, any history of hepatic/liver disease or renal disease, any history of cardiovascular diseases; women who are lactating (in addition to existing exclusion criteria for pregnancy). Co-I [name] (a physician) will review conditions/medications after the initial interview before the patient is enrolled to exclude risks of drug interactions or hepatotoxicity. UF/Shands staff and students will not be considered for enrollment. Presence of chronic pain will not be considered as a necessary condition for enrollment.

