Safety Monitoring and Stopping Criteria: Safety monitoring will occur during the initial baseline visit as well as throughout the participant's duration in the study, including a 1week follow-up contact after study termination. As noted below, the baseline assessment conducted during the first visit will include a brief physical exam (including vital signs) and a thorough medical and psychiatric history, including a review of past medical history, concomitant medications, inclusion/exclusion criteria, and potential contraindications. Safety monitoring will include active and passive surveillance procedures using preexisting safety monitoring guidelines. Participants will be assessed actively at each laboratory visit by study personnel using the side effects/adverse events checklist. Each participant will be read each side effect/adverse event from the checklist and instructed to self-report as yes (go) or no (no go). If a participant experiences any of the side effects/adverse events from the checklist provided at the baseline visit, study personnel will then contact the study physician ([name]) for consultation. The side effects/adverse events will be triaged as mild, moderate or severe, and a determination will be made by the study physician as to whether the side effect/adverse event is due to the investigational test article or some other circumstance (e.g. food poisoning). If the reaction or event is determined to be due to the investigational test article and graded moderate to severe by the study physician, the participant will then be instructed to stop participation and advised to seek medical care by their primary physician or hospital. (Refer to stopping

criteria below). Any serious adverse reaction or event will be followed until full resolution. All adverse reactions and events will be reported to the UF IRB within 24-48-hrs and documented in the participant's file (redcap). The PI/physician decides that the participant should be withdrawn for **safety reasons** (presence of active lesions in the oral cavity/sublingual region or suffering side effects or adverse events associated with the use of the investigational product). List of side effects and adverse reactions are listed below*

Stopping Criteria:

- 1. Participant is unwilling to continue in the study.
- 2. Lack of compliance with protocol.
- 3. Investigator or study sponsor stops the study for any reason.

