- 4. Participant is enrolled in error or lost to follow-up (lost to follow-up will be defined as a subject failing to attend planned study visits or failure to respond to contacts by study personnel after documented 2 attempts).

*Potential Side Effects and/or Adverse Events (AEs):

- 1. Feelings of anxiety (nervousness, restlessness or being tense, feelings of danger, panic, or dread), paranoia, or negative mood (depression or suicidal thoughts), or paranoia.
- 2. Suicidal ideation
- 3. Poor quality of sleep (persistent insomnia).
- 4. Feelings of extreme fatigue, sleepiness or drowsiness.
- 5. Feelings of nausea (upset stomach, vomiting or gastro-intestinal (GI) distress (e.g. diarrhea).
- 6. Change in or loss of appetite.
- 7. Feelings of light-headedness or dizziness.
- 8. Visual disturbances such as blurry/double vision.
- 9. Hypotension, hypertension, tachycardia, heart palpitations, syncope or dyspnea.
- 10. Development of a skin rash with redness and itching.

Each participant will be provided a detailed safety monitoring checklist of side effects and/or adverse reactions that they may potentially experience from ingesting the investigational product. Suicidal thoughts are not expected to be common, and there is no evidence that we know of about any association of CBD to suicide. In the unlikely event that a research participant would indicate suicidal thoughts or ideation during the visits or phone calls, they will be immediately interviewed for a formal assessment by [name] or Research Coordinator [name] (both are trained to perform such an assessment). If the assessment finds out they are not seriously suicidal, they can continue in the study. Reversely, if we the assessment finds the patient is serious about their intentions, we will either call 911 or have them agree to go to an ER for evaluation. The patient will be asked to to stop assuming CBD. In that case, we will continue to follow them if we do refer them somewhere. At the end of the study, we will try to assess whether there is any possibility that the CBD product itself is associated with the suicidal thinking or behavior.

[figure not shown]

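### Active sores in the mouth are grounds for withdrawal, but the printed adverse event list has no mouth item and no described post-baseline step asks about one

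*Combined protocol and SAP*

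**What the plan says.** All references are to Section 6, Research Plan, of the combined protocol and SAP.

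- **Route.** Under Investigational Product & Dosing Schedule, participants are to "administer the solution under the tongue (0.5 cc ~1/2 dropper) twice per day (BID"), from two 30 mL bottles.
- **Withdrawal reason.** Safety Monitoring and Stopping Criteria lets the PI/physician withdraw a participant for safety. Two alternative grounds are given: "presence of active lesions in the oral cavity/sublingual region", or side effects or adverse events associated with the product. The next sentence reads "List of side effects and adverse reactions are listed below", with an asterisk to the list.
- **The list.** Ten numbered items follow, from anxiety and low mood to the last, "Development of a skin rash with redness and itching".
- **Checks at visits.** "Each participant will be read each side effect/adverse event from the checklist and instructed to self-report as yes (go) or no (no go").
- **Checks elsewhere.** Between visits, participants are told to call if a checklist effect occurs. The call one week after completion also works from the checklist. Staff contact patients weekly, and the stated subject is missed doses.
- **Entry.** The first-visit assessment includes a brief physical exam and a review of "inclusion/exclusion criteria, and potential contraindications". The exclusion criteria, including the paragraph beginning "Further exclusion criteria will be: excluding subjects taking anti-seizure medicines, with any history of seizure disorder or head trauma", do not name oral lesions.

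**The concern.** A withdrawal rule works only if the triggering event becomes known. Here the mouth is the site of application, and the protocol itself treats an active lesion there as a reason to stop. As printed, however, the adverse event prompts cover mood, sleep, fatigue, gut, appetite, dizziness, vision, circulation and breathing, and skin. A participant who develops a sore under the tongue is not told by any printed text that it matters, and could go on applying oil to it. What is at stake is a small matter of participant safety. No outcome, sample size or error rate is affected.

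**Working it through.** No figure in the plan needs reproducing. The check sets the rule beside each described means of detection, then counts where a prompt could help.

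**1. The printed list.** The items are: (1) anxiety, paranoia or negative mood; (2) suicidal ideation; (3) poor sleep; (4) fatigue or sleepiness; (5) nausea or gastrointestinal distress; (6) appetite change; (7) light-headedness; (8) visual disturbance; (9) blood pressure, heart rhythm, syncope or dyspnea; (10) skin rash. Items 5 and 10 come closest, and neither covers a lesion of the oral mucosa. Items concerning the mouth: 0 of 10.

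**2. Other described steps after dosing starts.**

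| Step | Stated content | Prompts for a mouth lesion? |
|---|---|---|
| Visits 2 and 3 | Checklist items read out, yes or no | Only if the form has such an item |
| Self-surveillance | Call if a checklist effect occurs | Only if the form has such an item |
| Weekly contact | Missed doses | No, but one may be volunteered |
| Bottle photographs, about days 15 and 45 | Liquid level | No |
| One-week call | Checklist | Only if the form has such an item |

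The brief physical exam and the contraindication review are described for the first visit, so they cannot pick up a lesion that starts later.

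**3. Where a prompt could change dosing.** Inputs: 2 bottles of 30 mL, 0.5 mL per dose, 2 doses a day, visit 2 at day 26-34, visit 3 at day 56-64, 5 to 7 participants. No missed doses are assumed.

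- Supply: 2 × 30 / 0.5 = 120 doses per participant, or 120 / 2 = 60 days.
- Taken by visit 2: 26 × 2 = 52 to 34 × 2 = 68. Remaining: 120 − 68 = 52 to 120 − 52 = 68.
- Taken by visit 3: at day 56, 56 × 2 = 112, leaving 8. From day 60 the supply is used up, leaving 0.
- The one-week call follows completion, so no doses remain.

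Of the three scheduled readings after baseline, only visit 2 clearly falls while much dosing remains. That is 1 per participant, or 5 to 7 in the study. These counts describe exposure and opportunity, not harm. The documents give no incidence of oral lesions, so the number of participants affected cannot be estimated.

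**4. Staff time for one added line.** Assume 10 seconds per reading (range 5 to 20). Readings after baseline number 3 × 5 = 15 to 3 × 7 = 21.

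- At 10 seconds: 15 × 10 = 150 s (2.5 minutes) to 21 × 10 = 210 s (3.5 minutes).
- Over the range: 15 × 5 = 75 s (1.25 minutes) to 21 × 20 = 420 s (7 minutes).

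**The case against.** The strongest objection is that the working checklist cannot be seen. Participants are read a checklist, which the protocol calls detailed, and "Safety monitoring will include active and passive surveillance procedures using preexisting safety monitoring guidelines". A figure after the list is also not shown. Any of these may already hold a mouth item. This stands, and it limits the point to the printed text. A reader might infer that participants are asked about only the ten printed effects. The documents do not establish that the form equals the list.

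A reader might also infer that the protocol contradicts itself. It does not. Lesions and product-associated side effects are alternative grounds for withdrawal, and the list serves the second. A lesion's absence from a list of side effects is consistent with that. What remains is that the first ground has no described means of detection once dosing has begun.

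Three further cautions stand.

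- The interval before visit 2 is not a month without contact. Staff speak to patients weekly, and a sore could surface as the reason for a missed dose.
- The visit lists under Experimental Procedures are not exhaustive, since they omit the checklist that is required at every visit. They therefore do not show that the mouth is never inspected.
- At entry, the physician's review of conditions and medications and the brief physical exam reduce the chance of enrolling someone who already has a lesion.

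Finally, the documents report no oral lesions with this product. The side effects they cite (tiredness, appetite change, gut discomfort) come from trials in which the product was swallowed, so they say little about local effects under the tongue either way.

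**Conclusion.** The point holds at low severity, as a missing detection step in the printed text. The protocol makes an oral lesion grounds for withdrawal, 0 of 10 printed items concern the mouth, and no other described post-baseline step prompts for one. The benefit of a prompt is concentrated at visit 2, with 5 to 7 readings in all, and in self-reporting between visits. This rests on the printed wording alone; if the checklist form already has the item, only the printed list needs aligning. No claim is made about how often lesions occur or how many would be missed.

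**What to change.** Add *sore or lesion in the mouth or under the tongue* to the list under Potential Side Effects and/or Adverse Events and, unless it is already there, to the checklist form. Use it at visits and in participants' self-surveillance. A positive answer follows the existing route to the study physician, who can then apply the withdrawal reason.

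The cost is one checklist revision and, on the assumed reading time, about 2.5 to 3.5 minutes of staff time in the whole study (range 1.25 to 7). It adds no laboratory test or blood volume. An open question about anything else new, and a brief look under the tongue at visits 2 and 3, are optional preferences that the point does not depend on; they would add a little more time.
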